Another aspect to the study is evaluating the potential underlying mechanism by which NMES may improve lower limb IC symptoms. A number of studies evaluating IPC (Intermittent Pneumatic Compression) have shown functional and symptomatic benefit in patients suffering from IC [4]. Potential mechanisms include enhanced activation of the calf muscle pump increasing the venoarterial pressure gradient, thereby increasing the blood flow in the lower limbs. The drawbacks of IPC are that it is expensive and uses bulky equipment, the treatment takes substantial time (3-4 hours daily) and there is patient discomfort due to the pressure required to increase venous return. Lower limb NMES may mimic the effect of IPC by causing sufficient calf contraction to activate the calf muscle pump. Although haemodynamic assessment has shown significant increases in lower limb arterial blood flow measured by ultrasonography in healthy individuals that were using the Revitive IX device, further haemodynamic assessment in a robust clinical trial of NMES in IC patients will help advance our understanding and assist in developing future technology to optimise the use of this mechanism for patient benefit.

This study will enable robust research to determine definitive clinical efficacy, mechanistic evaluation and cost effectiveness of a novel intervention that will significantly impact care provision and outcomes for patients with PAD.

## 3. Study Objectives

The objective of the study is to assess the benefit of using a neuromuscular electrical stimulation device as an adjunct to the local standard care available at the study sites compared to local standard care alone.

The device is expected to increase the walking distance in patients with intermittent claudication, and to have an adjuvant benefit on the same when provided in addition to supervised exercise programmes. It is also expected to cause a reduction in pain symptoms and reduced likelihood of major intervention in late stage PAD.

Imperial Clinical Trials Unit	STATISTICAL ANALYSIS PLAN	NESIC
-------------------------------	---------------------------	-------

### **3.1 Primary Objectives**

The primary research objective is to assess the clinical efficacy of a NMES device as an adjunct to the local standard care available at the study sites in improving walking distance in patients with IC. The clinical efficacy will primarily be measured by a change in the Absolute Walking Distance (AWD) over the study protocol period, as measured by a standardised treadmill test.

### **3.2 Secondary Objectives**

Secondary outcomes, including validated Quality of Life (QoL) questionnaires and compliance data, will assist in modelling for economic evaluation of this intervention compared to standard treatment practice. This will be used to assess cost effectiveness. The health economic assessment will be done by [name] and thus is not covered in this SAP.

Analysis will also be carried out to understand the underlying mechanisms of change in clinical and subjective outcomes. This will take the form of lower limb gross and superficial haemodynamic assessment. These assessments will be undertaken using Duplex Ultrasonography (DU) and Laser Doppler Flowmetry (LDF), respectively.

## **4. Study End Points**

### **4.1 Primary Endpoint**

Absolute walking distance (AWD) measured by standardised treadmill testing at 3 months (the end of the intervention period).

### **4.2 Secondary Endpoints**

- Initial claudication distance (ICD)
- Quality of life (QoL): Intermittent Claudication Questionnaire (ICQ), EuroQoL 5D – 5L (EQ-5D-5L), Short Form 36 (SF-36)
- Haemodynamic assessment: Duplex ultrasonography, Laser Doppler Flowmetry (LDF), Ankle Brachial Pressure Index (ABPI)
- Health economic assessment
- Compliance with interventions
- Device experience questionnaire

## **5. General Considerations**

### **5.1 Study Design**

The NESIC trial is a pragmatic, multicentre two-arm randomised controlled study stratified by centre. There are 11 participating centres in England, distributed according to local therapy provision between SET and exercise advice only. Initially 5 SET centres and 6 exercise only centres recruited to the trial until all the SET sample of patients was recruited, subsequently 3 SET centres (Imperial, Bristol and Hull) also recruited patients for the exercise only group. Subject to any patient specific restrictions, all participants will receive the best medical therapy (BMT), which include exercise advice, and if the patient has cardiovascular risk factors, then they will aim to control this, e.g. smoking cessation, hypertensive medication and controlling diet.

### **5.2 Treatment**

#### **5.2.1 Supervised Exercise Therapy (SET)**

The Supervised Exercise Therapy program (SET) is carried out under the supervision of a healthcare professional and entails a circuit of lower limb specific exercises for a minimum of 30 minutes per week. The Supervised Exercise Therapy program (SET) is not standardized among the centres. The number of SET sessions varies from

8 to 36, depending on the number of SET sessions per week and the number of months it is practiced for. Attendance is recorded via patient diaries (See Appendix 1 for more information).

### 5.2.2 Neuromuscular Electrical Stimulation Device (NMES)

The Neuromuscular Electrical Stimulation device (NMES) is recommended to the patient to be used once a day for 30 minutes, 7 days a week, for 12 weeks (84 days). The time of the day that the device is used is left up to the patient and usage is recorded via patient diaries.

### 5.2.3 Exercises Advice (EA)

The participants will be given standard advice on exercise as per local guidelines. The recommended minutes per week varies between centres. In general, it is recommended to perform at least 30 minutes of physical exercise 3 - 5 times per week. (A set of specific exercises is provided for each patient). Participants will be provided with a diary to note the frequency and duration of their exercise activity.

## 5.3 Treatment Groups

Subjects will be randomised to one of 2 treatments: the inclusion of the NMES device together with the local available exercise therapy (NMES+LAET) versus just the local available exercise therapy (LAET). Depending on the type of centre, local available exercise therapy will consist of Supervised Exercise Therapy (SET) and Exercise Advise (EA) in SET centres or exercise advice alone in non-SET centres.

**Table 1 Summary of Treatment groups**

Type of centre	Treatment
SET Centre	Control 1: Best Medical Therapy (BMT) + Exercise Advise (EA) + Supervised Exercise Therapy (SET)
	Treatment 1: Best Medical Therapy (BMT) +Exercise Advise (EA) + Supervised Exercise Therapy (SET) + Neuromuscular electrical stimulation (NMES)
Non-SET Centre	Control 2: Best Medical Therapy (BMT) + Exercise Advise (EA)
	Treatment 2: Best Medical Therapy (BMT) + Exercise Advise (EA) + Neuromuscular electrical stimulation (NMES)

- Treatment duration: 3 months of device use
- Follow-Up duration: 12 months (follow-up visits at 3, 6, and 12 months).

## 5.4 Study Population

This study is open to all patients at the participating NHS sites with a diagnosis of IC and who meet all inclusion and exclusion criteria. The 11 sites have been selected with respect to their ability to provide SET. The protocol includes a list of the recruiting centres and specifies whether the centre provides SET, or only provides exercise advice (EA).

## 5.5 Eligibility Criteria

The patients participating in the study must meet the following inclusion and exclusion criteria:

### 5.5.1 Inclusion Criteria

- Capacity to provide informed consent
- Aged 18 or above
- Positive Edinburgh Claudication Questionnaire
- ABPI <0.9 or positive stress test (fall in ankle pressure >30mmHg, 40 secs post 1 min treadmill at 10% gradient, 4 km/h).

### 5.5.2 Exclusion Criteria

- Severe IC requiring invasive intervention as determined by the treating clinician
- Critical limb Ischaemia as defined by the European Consensus Document
- Co-morbid disease prohibiting walking on a treadmill or taking part in supervised exercise therapy.
- Popliteal Entrapment Syndrome
- Commenced vascular symptom specific medication in previous 6 months e.g. naftidrofuryl oxalate, cilostazol
- Pregnancy Participants must be of non-childbearing potential\* OR using adequate contraception for the duration of the study period and have a negative urine pregnancy test result
- Any implanted electronic, cardiac or defibrillator device
- Acute Deep Vein Thrombosis
- Broken or bleeding skin including leg ulceration
- Peripheral neuropathy
- Recent lower limb injury or lower back pain.
- Able to walk longer than 15 minutes on the study treadmill assessment \*\*
- Already using a NMES device†
- Have attended supervised Exercise therapy classes in the previous 6 months†

\*Defined as those who have no uterus, ligation of the fallopian tubes, or permanent cessation of ovarian function due to ovarian failure or surgical removal of the ovaries. A woman is also presumed to be infertile due to natural causes if she has been amenorrhoeic for greater than 12 months and has an FSH greater than 40 IU/L.

\*\*This criterion was initially classified as a screening failure in post-randomisation because it was not documented as exclusion criteria in the protocol. An amendment to the protocol to include this as an exclusion criteria was submitted on 16th September 2019. REC/HRA approval was granted on 18th October 2019.

†These criteria were not initially part of the exclusion criteria but were checked prior to randomisation and so were excluded. An amendment to the protocol was submitted on 16TH September 2019. REC/HRA approval was granted on 18th October 2019.

With permission of the participant the reasons for non-inclusion will be logged anonymously along with a minimum data set of age, sex and ABPI and reasons for exclusion. The anonymized pre-screening logs will be transferred to the Trial Coordinating Centre for the purposes of monitoring recruitment. Written informed consent will be obtained before the subject is enrolled in the study.

### 5.6 Blinding

This study is unblinded.

### 5.7 Sample Size

Assuming that the mean AWD in the control group is 200m at 3 months [5] and a common equal standard deviation of 120m [6], without considering the dropout rate, it is estimated that a sample size of 172 participants (86 per group) will have 90% power with a two-sided alpha = 0.05 to detect a difference of 60m in the mean absolute walking distance at 3 months between the intervention and the control group.

Assuming a 10% dropout rate, the sample size required for this study is 192 participants; 96 in each arm.

## 5.8 Schedule of Time and Events

The actual study commenced recruitment on 21st March 2018 and was expected to recruit for 15 months but was extended to finish on 31st March 2020 (granted by REC/HRA). However recruitment was temporarily paused on 20th March 2020 due to COVID-19. The last follow up will end one year after the recruitment of the last patient. The summary table of Visit Schedule and the summary of Treatment time are displayed in Section 5.8.1 and Section 5.8.2 respectively.

### 5.8.1 Summary of Visit Schedule

Visit	Screening	Baseline*	Treatment Phase 0 - 3 months	Follow-up (months) †		
	1	2		3	4	5
				3 months	6 months	12 months
Informed consent	x					
Pregnancy Test	x					
Ankle Brachial Pressure index (ABPI) / positive stress test	x			x	x	x
Edinburgh Claudication Questionnaire						
Medical History	x					
Drug history	x			x	x	x
Peripheral pulse examination	x			x	x	x
Other exclusion criteria	x					
Randomisation		x				
Demography		x				
Vital Signs		x				
Quality of life questionnaires: EQ-5D-5L /SF-36 /ICQ		x		x	x	x
Treadmill test (ICD/ AWD)		x		x	x	x
Duplex Ultrasonography		x 		x 		
Laser Doppler Flowmetry		x 		x 	x	x
NMES training		x				
SET booking		x				
Compliance Diary (SET/device/EA)		x		x		
Resources use diary		x	x	x		
Weekly text messages			x			
Data logger		x	x			
Device experience questionnaire				x		
Safety reporting			x	x	x	x

Baseline and screening visit occur on the same day if both the researcher and participant agree that informed consent has been adequately considered with time to ask questions

women of childbearing potential a required to take a urine pregnancy test

At rest and during device use in device arm

[figure not shown]
NMES treatment groups only

SET centres only

For first 3 months (treatment period) or for whole duration they are completing SET classes (whichever is longer)

[figure not shown]
 The follow up information may be collected remotely (i.e. over the telephone completely or in combination with postal questionnaires) in the event that the participant is unable to attend the appointment in the clinic or the site is unable to accommodate the onsite visit due to COVID-19.

### 5.8.2 Summary of Treatment Plan

Details about patient enrolment, follow-up and inclusion in analysis is provided in the CONSORT diagram below.

## 5.8.3 Patient Flow CONSORT diagram

Imperial Clinical Trials Unit	STATISTICAL ANALYSIS PLAN	NESIC
-------------------------------	---------------------------	-------

## 5.9 Randomization

Once eligibility has been confirmed, subjects will be randomised to one of the two arms of the study and assigned a pseudonymised study number unique to each individual enrolled in the trial.

Randomisation will take place via the InForm system (the electronic case report form database for the study), which will be programmed with a randomisation schedule provided by an independent statistician. Randomisation will be blocked with random block sizes and stratified by centre.

SET CENTRE randomisation:

- Control 1: EA + SET
- Treatment 1: EA + SET + NMES

Non-SET CENTRE randomisation:

- Control 2: EA
- Treatment 2: EA + NMES

## 6. Analysis Sets

### Definition of Primary Analysis

The primary analysis will estimate the difference in the absolute walking distance at 3 months (AWD3M) between the two treatment groups NMES + local available exercise therapy (NMES+EA or NMES+EA+SET) vs. local available exercise therapy (EA or EA+SET).

There are two populations of interest: the intention to treat (ITT) population for efficacy and the per-protocol (PP) population for efficacy.

#### 6.1 Intent-to-Treat Population

This population includes all patients, with eligibility confirmed at screening that were randomised regardless of treatment adherence. The follow-up period for these patients will be 12 months in total (with primary endpoint measured at 3 months). This analysis set will exclude all those who specifically asked to be withdrawn and their data not to be used for the trial.

If there is a difference in SET uptake, measured by number of attended SET classes over the centre specific prescribed attendance target, between the groups (NMES+SET+EA vs SET+EA), then we will conduct an appropriate analysis using CACE methods that do take into consideration non-compliance.

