### 1.4 Summary of current research

SETs are known to significantly improve the absolute walking distances in patients suffering from IC.

A Cochrane systematic review of the impact of SET on walking distances was carried out by Bendermacher et al in 2006 (5), and was repeated with updated

Imperial Clinical Trials Unit	NESIC Clinical Study Protocol V6.0 24/03/2020	Form Number CR001A-T
-------------------------------	---	-------------------------

study data in 2013 by Fokkenrood et al (6). The latter review included randomised controlled trial (RCT) data comparing SET to non- SET management in patients with IC. Fourteen studies with a total of 1002 participants were randomised and followed up for a duration between 6 weeks and 12 months, with the primary outcome measure being absolute walking distance (AWD) measured by treadmill testing. There was a significant improvement of AWD with a size effect of 0.69 (95% Confidence Interval (CI) 0.51-0.86) and 0.48 (95% CI 0.32-0.64) at 3 months and 6 months respectively. On average, there was an improvement in AWD of approximately 180 metres in the SET group (6).

There is a strong evidence base in favour of SET, contributing to the NICE recommended first line therapy strategy in all IC patients. Despite these benefits, SET remains underutilised in the UK. A postal audit published by Shalhoub et al in 2009 (7) showed that only 24% of 84 responding UK vascular surgeons had access to a SET for their IC patients.

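### SAP 6.1 ties its only CACE to a between-arm difference in SET attendance, but arm randomises NMES and cannot identify a SET effect, and the target of a CACE for NMES use is left undefined

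*SAP*

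**What the plan says.** - SAP 6.1 states the condition as "If there is a difference in SET uptake, measured by number of attended SET classes over the centre specific prescribed attendance target", and continues: "between the groups (NMES+SET+EA vs SET+EA), then we will conduct an appropriate analysis using CACE methods that do take into consideration non-compliance". The section does not say what size of difference counts, whether it is tested, which treatment received defines a complier, what the instrument is, or what effect is being estimated. No other part of the SAP text plans a CACE.
- SAP 5.9 randomises SET-centre patients to EA + SET or to "Treatment 1: EA + SET + NMES". The randomised element is NMES; SET is in both arms. SAP 5.6 adds: "This study is unblinded".
- SAP 13.3.3 defines an NMES complier as a patient with at least 75% of 2520 minutes (1890), but 6.1 does not refer to it.
- SAP 8.8.1 handles compliance by a subgroup of compliers, which is not a CACE. The composite definition in SAP 7.2 has different components in each arm, so it does not describe receipt of one common treatment.
- Protocol 8.3 promises causal methods for compliance with NMES, SET and EA, and Protocol 8.3.2 plans a CACE for the haemodynamic outcomes. Neither is conditional on SET uptake.

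**The concern.** A CACE that uses randomised arm as the instrument rests on exclusion: arm may affect walking distance (AWD) only through the treatment whose receipt is modelled. SAP 6.1 names SET uptake and no other compliance measure, so an analyst following it would most naturally take SET attendance as the treatment received. Arm also delivers NMES, which the trial expects to improve AWD, so exclusion fails on the trial's own hypothesis.

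If the analyst takes NMES use instead, the trigger means that the arms have been seen to differ in a second active treatment. The plan does not say whether that difference belongs to the effect of interest. In an open-label trial, patients may attend fewer or more classes because of what they were allocated, whether or not they use the device.

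Non-adherence to the device, which is non-compliance with what was actually randomised, does not activate the analysis at all. At stake is a secondary figure that would be read as the effect accounting for compliance.

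**Working it through.** **Plan's own figure.** The documents state no CACE result. The 60 m used below is the design target in SAP 5.7, to "detect a difference of 60m in the mean absolute walking distance at 3 months between the intervention and the control group". That calculation reproduces: SD 120 m, two-sided 5%, two-sample t, 86 per arm, power 0.903; 172/0.9 = 191.1, rounded up to 192.

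**Inputs**
- tau = 60 m, NMES effect in device users (SAP 5.7).
- beta = 180 m, effect of full SET attendance. Protocol 1.4 reports from a review that "there was an improvement in AWD of approximately 180 metres in the SET group". Benefit proportional to attendance is an assumption.
- p = 0.75, share of device-arm patients who use NMES. This is an assumption (range 0.50 to 0.90), and is not the SAP's 75%-of-minutes threshold.
- D = SET uptake in the device arm minus control. Values are assumed.

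**Formulas** (differences in means, ignoring treadmill censoring)
- ITT = tau x p + beta x D
- NMES use as treatment received: ITT/p = tau + beta x D/p
- SET attendance as treatment received: ITT/D = beta + tau x p/D

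The last equals beta only if tau = 0.

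| D | ITT (m) | NMES-defined (device-specific value 60) | SET-defined (value 180) |
|---|---|---|---|
| -0.20 | 45 - 36 = 9 | 12 | -45 |
| -0.10 | 45 - 18 = 27 | 36 | -270 |
| -0.05 | 45 - 9 = 36 | 48 | -720 |
| +0.05 | 45 + 9 = 54 | 72 | +1080 |
| +0.10 | 45 + 18 = 63 | 84 | +630 |
| +0.20 | 45 + 36 = 81 | 108 | +405 |

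Sensitivity at D = -/+0.10:
- p = 0.50: 24 and 96 m (NMES-defined); -120 and +480 m (SET-defined).
- p = 0.90: 40 and 80 m; -360 and +720 m.
- beta = 60 with p = 0.75: 52 and 68 m (NMES-defined).

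Simulation with 20,000 per arm at D = -0.10 gave about 36 m and about -270 m.

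**When the NMES-defined version is valid.** Its natural target is the total effect of using the device, including any change in attendance that use causes. At D = -0.10 and p = 0.75 the estimator returns 36 m, and the true complier total effect depends on the route:
- Attendance changes only through device use: 60 + 180 x (-0.10/0.75) = 36 m. Bias 0.
- Assignment shifts attendance equally in everyone: 60 - 18 = 42 m. Bias -6 m.
- Only never-users change attendance: 60 m. Bias -24 m.

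For scale, the unadjusted standard error with 48 per arm is 120 x sqrt(2/48)/0.75 = about 33 m.

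**The trigger.** With 48 per arm and an assumed SD of 0.30 in attendance share, the standard error of D is 0.30 x sqrt(2/48) = 0.061. For a true 10-point difference, first-stage F = (0.10/0.061)^2 = about 2.7 and power at 5% is about 37% (50% to 29% for SD 0.25 to 0.35). If there is no true difference, with 43 per arm and uptake (SD 0.30) limited to 0-1, an observed gap above 5 points occurs in about 39% of trials; a two-sided 5% test would trigger in about 5%. The rule does not say which applies. In SAP Table A6 one centre's target also spans six months, so its uptake can include classes after the 3-month outcome.

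**The case against.** - **The SAP commits to no estimator.** It says only that an appropriate CACE analysis will be done. This is correct, so it cannot be said that the plan will produce the SET-defined figures. But the sentence names SET uptake alone, and nothing in it steers the analyst away from that choice.
- **A SET difference need not bias an NMES CACE.** A reader might infer that no valid CACE exists once the trigger is met. The documents do not support that: if attendance changed only because the device was used, SET is a mediator and the NMES-defined estimate is unbiased for the total effect of use. Bias needs another route from assignment to attendance, which is plausible without blinding but not certain.
- **The trigger is not what breaks the SET-defined version.** That version fails because arm delivers NMES, whether or not uptake differs.
- **The ITT result stands.** A reader might infer that the CACE displaces it. SAP 6 and 8.2 make the ITT Tobit model primary, and SAP 6.3 also estimates the NMES effect within SET sites on an ITT basis. Nothing says that either gives way.
- **The inputs are partly assumed.** Device use, uptake differences and linearity are not in the documents, and courses run from 8 to 36 sessions. The sizes are therefore illustrative. The failure of arm as an instrument for SET does not depend on them.

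**Conclusion.** The point holds for a supplementary analysis in the SET stratum (96 of 192 planned, Protocol 3.2) and should be corrected before analysis. It does not touch the primary result.

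Arm cannot be an instrument for SET attendance if NMES has any effect. Under the stated assumptions the result is -270 m or +630 m against 180 m at uptake differences of -/+10 points. A CACE for NMES use is a coherent quantity if its target is declared as the total effect of device use, subject to bias (here 0 to -24 m at D = -0.10) where assignment changes attendance by other routes. It is not the device effect with SET held fixed (36 or 84 m against 60 m). The trigger is undefined in size and attached to a non-randomised treatment, while NMES non-adherence does not trigger anything.

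**What to change.** Replace the conditional sentence in SAP 6.1 with text to this effect:

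1. SET attendance is reported by arm, with the difference and its 95% CI. Any difference is treated as part of the effect of offering NMES.
2. Randomised arm is not used as an instrument for SET attendance.
3. Any CACE is defined by NMES use at the 75% threshold in SAP 13.3.3, with arm as instrument and the total effect of device use as target. It is reported beside the ITT estimate and does not depend on SET uptake. State its assumptions, including that use below the threshold has no effect.
4. In SET patients, add a sensitivity range: (ITT - D x assumed SET benefit)/NMES complier share, with the benefit running from 0 to 180 m and linearity stated as an assumption. In the example this gives 27/0.75 = 36 m to (27 + 18)/0.75 = 60 m at D = -0.10, and 63/0.75 = 84 m to (63 - 18)/0.75 = 60 m at D = +0.10. Non-SET patients have no SET-class path and need no such range.

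Reconcile Protocol 8.3, which promises causal methods for SET and EA compliance as well, by recording in the SAP why the randomised arm cannot support a CACE for SET attendance and how the rest of that promise will be met.

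The cost is a few lines of SAP text and one calculation on data already collected.
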